3.2. Study Duration for Subjects

Study participation for each individual subject will be approximately 4 weeks in the Screening Period, at least 48 weeks in the DBTP, maximum 15 months in the OLP and 5 years from first dose of IP, or 3 years from last dose (whichever occurs later) in Post-treatment Follow-up Period until the End of Trial (Section 3.3)

End of Treatment for each individual subject is defined as the date of the last IP dose in the DBTP or OLP, whichever occurs later.

End of Study for each individual subject should occur after the study is unblinded (ie, 48 weeks after last subject has received the first dose of IP), and the OLP or the PTFP have been completed, as appropriate, or at the End of Trial as defined in Section 3.3, whichever occurs later.

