- Hemoglobin fractions (by central lab; predose sample on dosing days) (as detailed in Section 6.7)
- Administration of luspatercept on Day 1 of each dosing cycle
- QoL Questionnaire (NTDT-PRO with PGI-S for validation): to be completed by the subjects 7 days prior to dosing, every other dose

- QoL Questionnaires (SF-36 v2, FACIT-F, and PGI-C): to be completed by the subjects before knowing the Hb test result on dosing visits indicated in Table 3
- Only at Week 144 post first dose, if applicable, ie, for subjects who entered the OLP prior to reaching Week 144 in the DBTP:
 - Echocardiography or MRI (same technique to be used throughout the study): to assess LVEF and TRV
 - MRI for LIC (mg/g dw) (as detailed in Section 6.1) - only at Week 144 post first dose, if applicable
 - MRI for extramedullary masses - only at Week 144 post first dose, if applicable, only subjects with medical history of masses
 - MRI or abdominal ultrasound for spleen measurement (as detailed in Section 6.1) - only at Week 144 post first dose, if applicable
 - Bone imaging DXA scan (as detailed in Section 6.1) - only at Week 144 post first dose, if applicable
 - 6MWT (6-minute walk test)- only at Week 144 post first dose, if applicable

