4.1.2. Double-blind Treatment Period

Subjects will enter the Double-blind Treatment Period (DBTP) once they have completed the required assessments in the Screening Period and been randomized via the Interactive Response Technology (IRT) system. The DBTP will begin on Dose 1 Day 1 and end when all subjects have completed 48 weeks of treatment or have discontinued earlier. At that time, the study will be unblinded.

Subject randomization will occur via the IRT system and Dose 1 Day 1 should be scheduled within 3 days of randomization (can be on the same day as randomization). Eligible subjects will be randomized at a ratio of 2:1, luspatercept versus placebo, at a starting dose level of 1.0 mg/kg administered by subcutaneous (SC) injection once every 3 weeks. The maximum total dose per administration is 120 mg.

Best supportive care is allowed in both the luspatercept and placebo groups. This will include RBC transfusions, iron-chelating agents, use of antibiotic therapy, antiviral and antifungal therapy, nutritional support as needed, and other medications that are not prohibited, thus minimizing the safety risk to patients.

After the study is unblinded, and after DMC's recommendation:

- Subjects who received placebo and have been assessed as per protocol up to 48 weeks after the first dose of investigational product (IP) (even if the IP is discontinued before completing 48 weeks of treatment), may access the Open Label Phase (OLP) to receive luspatercept for a maximum 15 months before moving to the rollover protocol for longer treatment.

- Subjects receiving luspatercept may continue their treatment in the OLP for maximum 15 months before moving to the rollover protocol for longer treatment (i.e. 5 years from Dose 1, or until treatment discontinuation, whichever occurs later).
- Subjects who received luspatercept and discontinued the IP in the DBTP may continue and/or complete the long-term follow-up of 5 years from first dose of IP, or 3 years from last dose (whichever occurs later), to complete the Post-Treatment Follow-Up Period (PTFP) under the rollover protocol in this study until the End of Trial.

Subjects may be discontinued from treatment and/or the study decided by the treating physician.

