 - c. Average of all Hb measurements in Weeks 14-25 (Day 93 to Day 176) if Weeks 14-25 has ≥ 3 Hb measurements
 - d. When the number of Hb measurements is less than 3 among Weeks 13-24, Weeks 12-23, and Weeks 14-25, then choose the largest number of Hb measurements in the following order as Hb at Week 13-24:
 - 1) Hb in Week 13-24
 - 2) Hb in Week 12-23

- 3) Hb in Week 14-25
 - e. Otherwise, missing
 - Weeks 37 - 48 interval: Same rule as Week 13-24 interval
- The calculation of weekly NTDT-PRO scores is detailed in Section 18.3.1. The 12-week interval score is obtained by averaging all the weekly scores (at least one non-missing) in these 12 weeks. If all the weekly scores in these 12 weeks are missing, the 12-week interval score is then declared missing.

This SAP addresses efficacy and safety endpoints during the double-blinded treatment period (including the initial 48-week treatment period for all subjects and the long-term treatment period for early enrolled subjects). The database will be locked upon all subjects completed 48 weeks of the double-blind treatment period or discontinued before reaching 48 weeks. All the data collected up to data cutoff date will be used for summary. Data selection rules will be applied in each summary panel as needed, please refer to individual part for details.

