9 STUDY TREATMENTS AND EXTENT OF EXPOSURE

Subjects will be assigned to one of following regimens during treatment phase:

- Luspatercept starting dose level 1.0 mg/kg SC once every 21 days
- Placebo SC once every 21 days

Study treatment and extent of exposure summaries will be provided based on the safety population. Descriptive statistics will be provided for treatment duration, number of doses received per subject/treatment and average number of days per dose by treatment group and total. The number and percentage of subjects will be summarized for maximum dose level received, and dose level reduced to by treatment group and total. Corresponding listing will be provided.

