11.1 Adverse Events

Adverse events will be analyzed in terms of treatment-emergent adverse events (TEAEs) which are defined as any AEs that begin or worsen on or after the start of study drug through 63 days after the last dose of IP (i.e., AE start date on or after the first dose date and within last dose date + 63). In addition, an AE that occurs beyond this timeframe and that is assessed by the investigator as possibly related (suspected) to study drug will be considered as treatment-emergent.

All AEs will be coded using the Medical Dictionary for Regulatory Affairs® (MedDRA) dictionary. The incidence of TEAEs will be summarized by MedDRA system organ class (SOC) and preferred term (PT). The AE tables will be sorted by SOC and PT (within SOC) in descending frequency within the luspatercept group. If a subject experiences multiple AEs under the same PT (or SOC), then the subject will be counted only once for that PT (or SOC).

The intensity of AEs will be graded 1 to 5 according to the National Cancer Institute Common Terminology Criteria for Adverse Events (CTCAE) Version 4.0. If a subject experience the same AE more than once with different toxicity grades, then the event with the highest grade will be tabulated in “by grade” tables. In addition, AEs with a missing intensity will be presented in the summary table as an intensity category of “Missing” only if the same event category has no other valid grades.

Tables summarizing the incidence of TEAEs will be generated for each of the following by treatment group (if not otherwise specified, the summary is by SOC and PT):

- TEAEs;
- TEAEs by SOC only;
- Treatment-related TEAEs;
- Serious TEAE;
- Treatment-related serious TEAEs;
- TEAEs by CTCAE maximum severity
- Treatment-related TEAEs by CTCAE maximum severity
- TEAE with CTCAE Grade ≥ 3 ;

- Treatment-related TEAE with CTCAE Grade ≥ 3 ;
- TEAEs leading to study drug discontinuation;
- Treatment-related TEAEs leading to study drug discontinuation;
- TEAEs leading to study drug dose reduction;
- Treatment-related TEAEs leading to study drug dose reduction;
- TEAEs leading to death;
- Treatment-related TEAEs leading to death;
- Most frequent TEAEs by PT ($\geq 5\%$ in PT frequency of all subjects or subjects from any treatment group);
- Most frequent TEAEs by SOC ($\geq 5\%$ in SOC frequency of all subjects);
- Most frequent TEAEs by SOC and high level term (HLT) ($\geq 5\%$ in HLT frequency of all subjects);

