11.3 Other Adverse Events That Require Safety Analysis

Other adverse events that require safety analysis include AEs that fall under the “Embolic and Thrombotic Events and Thrombophlebitis” SMQ category and AEs with PT “Bone pain” and ‘Hypertension’.

Similar to AESI, summary will be provided for AEs that fall under the “Embolic and Thrombotic Events and Thrombophlebitis” SMQ category by preferred term. For “Bone pain” events, number of subjects with bone pain events by worst CTCAE grade will be provided from grade 1 to grade 5. The number and percentage of subjects with bone pain occurred during the first 24 weeks and after 24 weeks will be provided. Summary statistics will also be provided for time to first bone pain, total duration of bone pain (in days), total duration of bone pain that occurred during the first 24 weeks (in days), and total duration of bone pain that occurred after 24 weeks (in days). Total duration of bone pain is defined as sum of all bone pain duration within a subject, excluding overlapped period. Same summaries are also conducted on ‘Hypertension’.

The “Embolic and Thrombotic Events and Thrombophlebitis” SMQ category analysis will include subgroup analysis by splenectomy status, platelet above ULN, concomitant medications, and comorbidities as needed.

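### TEAE tables give crude percentages over a double-blind period of varying length, with no person-time rate or common 48-week table to guard against unequal time on treatment

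*SAP*

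**What the plan says.** **Length of the period.** SAP 4.1.2 sets a common calendar end: "The DBTP will begin on Dose 1 Day 1 and end when all subjects have completed 48 weeks of treatment or have discontinued earlier". Protocol 3.2 plans "at least 48 weeks in the DBTP" for each subject. SAP 5.1 describes the period it covers as "including the initial 48-week treatment period for all subjects and the long-term treatment period for early enrolled subjects". The dose-count categories in SAP 9.2 run to more than 32 doses, and Protocol 6.3 schedules Week 144 assessments in the open-label phase "for subjects who entered the OLP prior to reaching Week 144 in the DBTP", so it allows for a subject passing Week 144 while still blinded.

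**Which data count.** SAP 5.1 states that "All the data collected up to data cutoff date will be used for summary", and adds that selection rules will apply panel by panel where needed. For adverse events the rule is the TEAE window in SAP 11.1: first dose to 63 days after last dose, plus later events judged related. It has no Week 48 limit. The limit in the opening text of SAP Section 10 is confined to the endpoints of that section, which are efficacy endpoints.

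**How TEAEs are summarised.** SAP 11.1: "Tables summarizing the incidence of TEAEs will be generated for each of the following by treatment group". A subject counts once per preferred term or system organ class, and SAP 5.1 prescribes number and percentage for discrete variables.

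**What else is planned.** SAP 9.1 to 9.3 describe treatment duration, doses and dosing interval by arm. SAP 11.2 gives descriptive time to first AESI. For bone pain, SAP 11.3 adds time to first event, total duration and a split by period: "The number and percentage of subjects with bone pain occurred during the first 24 weeks and after 24 weeks will be provided". The same summaries apply to hypertension.

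**The concern.** The percentage of subjects with at least one event rises with time at risk even at a constant underlying rate. Here time at risk varies widely between subjects, and it is partly an outcome of treatment, because stopping ends it (after a 63-day tail). If one arm stops sooner, its crude percentages fall for that reason alone. The documents name routes in both directions. SAP Section 6 lists lack of efficacy as a reason for stopping treatment, and SAP 4.4 assumes 10% response on placebo against 50% on luspatercept, so placebo exposure could be shorter. Protocol 11.1 lists related serious AEs, and more than two dose reductions for related AEs, as reasons to stop, so luspatercept exposure could be shorter.

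In the first case luspatercept would appear to carry an excess risk that does not exist. In the second a real excess could disappear. The tables affected include serious and Grade 3 or higher TEAEs, malignancy, embolic and thrombotic events, bone pain and hypertension, which carry the main safety conclusions.

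**Working it through.** The plan states no figure on this point, so there is none to reproduce. The check has three steps.

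**1. Span of exposure.** Inputs: the more-than-32-dose category (SAP 9.2) and the regimen in SAP Section 9, "Luspatercept starting dose level 1.0 mg/kg SC once every 21 days", with placebo on the same interval. The 33rd dose falls 32 × 3 = 96 weeks after the first, and 33 dosing intervals cover 33 × 3 = 99 weeks. Subjects who stop early have less than 48 weeks.

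**2. Dependence of a crude percentage on time.** At a constant hazard λ per year, the percentage with an event by week w is 1 − exp(−λw/52.18). With λ = 0.25 (assumed):

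- 48 weeks: 20.5%
- 72 weeks: 29.2%
- 99 weeks: 37.8%

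**3. Effect of unequal discontinuation.** The documents give no AE hazard, exposure by arm or enrolment length, so all of these are assumptions:

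- potential follow-up F uniform from 48 weeks to Fmax, with Fmax 100 or 144 weeks, the same in both arms
- time to discontinuation D exponential
- time at risk T = min(D + 9 weeks, F), since the cutoff ends the 63-day tail for subjects still on treatment
- crude percentage = mean of 1 − exp(−λT), with λ in the same time unit as T
- exposure-adjusted rate = expected first events ÷ expected person-time to first event. Person-time per subject is (1 − exp(−λT))/λ, so this ratio returns λ whatever the pattern of stopping.

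Equal hazards in both arms, luspatercept 10% discontinued by Week 48:

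| λ per year | Fmax (weeks) | Placebo discontinued by Week 48 | Crude %, luspatercept vs placebo | False difference (points) |
|---|---|---|---|---|
| 0.25 | 100 | 10% | 28.0 vs 28.0 | 0.0 |
| 0.25 | 100 | 20% | 28.0 vs 26.2 | 1.7 |
| 0.25 | 100 | 40% | 28.0 vs 22.8 | 5.2 |
| 0.25 | 144 | 20% | 33.5 vs 30.7 | 2.8 |
| 0.25 | 144 | 40% | 33.5 vs 25.5 | 8.0 |
| 0.1 | 100 | 20% | 12.4 vs 11.6 | 0.8 |
| 1.0 | 144 | 40% | 77.4 vs 64.4 | 13.0 |

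Differences are taken before rounding. The last two rows are the extremes over hazards 0.1 to 1.0 and placebo discontinuation of 20% to 40%. The exposure-adjusted rates are equal between arms in every row.

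Masking: take a true hazard ratio of 1.3 (0.325 vs 0.25 per year), with 40% discontinued on luspatercept and 10% on placebo. The crude percentages are 28.3% vs 28.0% (Fmax 100) or 31.4% vs 33.5% (Fmax 144). The exposure-adjusted rates stay at 0.325 vs 0.250.

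**The case against.** The strongest reply is that the harm is conditional and the documents do not show the condition. Randomization and a common calendar end make potential follow-up alike in expectation. SAP 4.4 assumes a single 10% dropout rate, not one per arm, and equal discontinuation gives no false difference. This stands. A reader might infer that the planned safety comparison is biased as it is; the documents do not support that.

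A reader might also infer that nothing but a count and percentage is reported. That is not so. Time to first event is planned for AESI, bone pain and hypertension, and the first-24-week rows for the latter two are a fixed common window. Treatment duration by arm will also expose any gap. But duration is never used as a denominator, the other items cover only a few event types, and the rows after Week 24 have no end point. SAP 11.3 gives no denominator for those rows. Under the general convention in SAP 5.1 it would be the full safety population, including subjects already off treatment.

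The tables are descriptive: neither SAP 11.1 nor Protocol 9.7 plans a between-arm test of AEs. The risk is therefore misreading, not an invalid test.

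Very large distortions should not be inferred either. With Fmax 100, mean exposure cannot exceed (48 + 100)/2 = 74 weeks even with no dropout. With Fmax 144, a contrast of 90 against 60 weeks needs roughly 6% against 38% discontinued by Week 48.

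Finally, it is tempting to confine crude counts to 48 weeks. That would drop late malignancies and thromboembolic events from the tables, where late counts matter most.

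**Conclusion.** The point holds as a gap in the safety analysis that is worth closing, not as a demonstrated bias. TEAEs are summarised as crude percentages over a window that differs between subjects and can extend past 96 weeks. No visible part of SAP Section 11 or Protocol 9.7 provides person-time or a common cut. If arms differ in discontinuation (10% against 20% to 40% by Week 48, assumed), the false crude difference at equal hazards is about 1 to 13 points. Its direction follows whichever arm stays on treatment longer, and it vanishes if discontinuation is equal. These figures rest on a constant hazard, exponential discontinuation and uniform staggered entry, none of which the documents supply. The span past 96 weeks is inferred from the dose categories and dosing interval. The finding of absence covers the visible text only, since parts of the SAP are removed or redacted. Whether exposure is balanced will not be known until unblinding, which is the reason to fix the method beforehand.

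**What to change.** Keep the full-period crude tables. In SAP 11.1 to 11.3, for all TEAEs, serious, Grade 3 or higher, treatment-related, AESI, embolic/thrombotic, bone pain and hypertension, add:

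1. First events per 100 subject-years with 95% CI by arm. Person-time runs from first dose to the earliest of first event, last dose + 63 days, death or data cutoff. Related events after day 63, which SAP 11.1 counts as treatment-emergent, are reported separately so that numerator and person-time match.
2. A TEAE table restricted to the first 48 weeks.
3. For the bone pain and hypertension rows after Week 24, subjects still at risk at Week 24 as the denominator.

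The cost is SAP wording and a few more tables; the dates needed are already collected. The rates assume a constant hazard and can dilute early-onset events in the arm with longer exposure, so they should be read beside the 48-week table.

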5.2. Analysis Populations

A summary of analysis populations will be presented by treatment group and total.

5.2.1. Intent-to-Treat Population

The intent-to-treat (ITT) population will consist of all randomized subjects regardless of whether or not the subject received IP. All efficacy analyses will be conducted for the ITT population and will be analyzed based on randomization treatment.

5.2.2. Per Protocol Population

Subjects in the ITT who have taken at least 1 dose of IP and do not have important protocol deviations as described in Section 7 prior to database lock. The Per Protocol population might be used in addition to ITT population to analyze primary and key secondary endpoints.

5.2.3. Safety Population

The safety population will consist of all subjects who were randomized and received at least one dose of IP. Subjects will be included in the treatment group corresponding to the IP they actually received.

5.2.4. Health-related QoL Evaluable Population

The Health-related QoL (HRQoL) evaluable population consists of all subjects in the ITT population with a valid health-related QoL assessment at baseline (screening) and at least one valid postbaseline assessment.

6. SUBJECT DISPOSITION

The total number of subjects screened and total number of subjects with screen failure will be summarized and listed. Reasons subjects did not qualify for the study will be displayed by category. A corresponding listing will be provided.

A summary of subject disposition will be presented by treatment group and total for ITT, Per Protocol, HRQoL and safety populations.

Subject disposition summary will present the number and percentage of subjects for the following categories:

- subjects who were randomized,
- subjects who received treatment,
- subjects who discontinued study treatment,
- subjects whose treatment were ongoing,
- subjects who completed 24 weeks of treatment,
- subjects who completed 48 weeks of treatment,
- subjects who discontinued from the study by treatment group and total.
- the reasons for discontinuation of study treatment
- the reasons for discontinuation of study participation

All percentages will be based on the number of subjects randomized using the ITT, Per Protocol, HRQoL, or safety populations.

The reasons for treatment discontinuation will be collected on the electronic case report form (eCRF) and summarized for all treated subjects based on the following categories:

- Death
- Adverse event
- Pregnancy
- Progressive disease
- Lack of efficacy
- Recovery
- Withdrawal by subject
- Non-compliance with study drug
- Lost to follow-up
- Study terminated by sponsor

- Transition to commercially available treatment
- Physician decision
- Site terminated by sponsor
- Protocol deviation
- Transition to rollover Protocol
- Failure to meet treatment criteria
- Other: dose is delayed for more than 15 weeks due to AEs (including case of elective surgery/hospitalization)
- Other

The reasons for study discontinuation will be collected on the eCRF (only when FUP period is not completed) and will be summarized for all randomized subjects based on the following categories:

- Death
- Adverse event
- Pregnancy
- Lack of efficacy
- Withdrawal by subject or parent/guardian
- Non-compliance with study drug
- Lost to follow-up
- Study terminated by sponsor
- Transition to commercially available treatment
- Physician decision
- Disease relapse
- Protocol deviation
- Transition to rollover protocol
- Other

A summary of subjects enrolled by geographic region, country, and site will be provided in a separate table by treatment group and total.

A subject disposition listing will be provided.

7. PROTOCOL DEVIATIONS AND IMPORTANT PROTOCOL DEVIATIONS

The protocol deviations and important protocol deviations will be identified and assessed by clinical research physician or designee following company standard operational procedure. An important protocol deviation occurs when there is any departure from the approved protocol that impacts the safety, rights, and/or welfare of the subject; or negatively impacts the quality or completeness of the data; or makes the informed consent document/form inaccurate. Important protocol deviations are identified based on blinded data reviews of deviation log throughout the study and are finalized prior to database lock.

The number and percentage of the subjects with any protocol deviation, or important protocol deviation will be provided for the ITT population respectively by treatment group and total. For important protocol deviations, the number and percentage of subjects within each subcategory will be summarized as well.

All protocol deviations will be listed for the ITT population.

